5.2.7. Date of Last Contact

The date of last contact will be derived for patients not known to have died at the data cutoff date using the latest complete date (ie, imputed dates will not be used in the derivation) among the following:

- All patient assessment dates (eg, blood draws (laboratory, Pharmacokinetics (PK)), vital signs, physical exam, performance status, ECG, Echocardiograms (ECHO)/multigated acquisition (MUGA) scans, tumor assessments, Mood and Suicidal Ideation assessment);
- Start and stop dates of concomitant therapies including non-drug treatments or procedures;
- Start and end dates of anti-cancer therapies administered after study treatment discontinuation including systemic therapy, radiation, and surgeries;
- AE start and end dates;

- Last date of contact collected on the ‘Survival Follow-up’ CRF (do not use date of survival follow-up assessment unless status is ‘alive’);
- Study treatment start and end dates;
- Date of discontinuation on disposition CRF pages (do not use if reason for discontinuation is lost to follow-up or death).

Only dates associated with actual examinations of the patient will be used in the derivation. Dates associated with a technical operation unrelated to patient status such as the date a blood sample was processed or dates when data were entered into the CRF will not be used. Assessment dates after the data cutoff date will not be applied to derive the last contact date.

5.2.8. Measurable Disease

A patient will be considered to have measurable disease if there is at least one target lesion identified at baseline meeting the following criteria:

- Non lymph node lesions with longest diameter ≥ 10 mm by CT scan ;
- Non lymph node lesions with longest diameter ≥ 10 mm caliper measurement by clinical exam (lesions which cannot be accurately measured with calipers should be recorded as non-measurable);
- CNS lesions with longest diameter ≥ 5 mm provided by gadolinium contrast enhanced MRI;
- Lymph nodes with short axis ≥ 15 mm when assessed by CT.

5.2.9. Tumor Assessment Date

Tumor assessment dates will be assigned differently for ICR assessment and for investigator’s assessment of tumor data.

For analyses of ICR assessments, the date of tumor assessment will be determine based on the radiologist assessments at each nominal timepoint and will be provided on listings as the associated date of response/progression at nominal timepoints. These dates will also be used for censoring in time to event analyses; however, the date of progression and response as provided by the independent radiologist will be used in time to event endpoint analyses as the independent radiologist provided an overall assessment of best response and date of progression based on a review of each nominal timepoint and additional clinical information available for the determination of the date of response/progression.

For analyses based on investigator’s assessment when response/progression are derived programmatically from the target lesions measurements, non-target lesions status, and new lesions recorded on the CRF, the date of tumor assessment should be derived as the earliest scan/assessment date. Since tumor assessments are captured on a log CRF page, a clustering algorithm for grouping scans will be used:

Each cluster represents an actual visit. For each patient, the number of clusters is equal to the maximum number of assessments available among all target and non-target lesions. SAS procedure, Proc Fastclus, is applied to a variable that represents the days from the date of first dose to the date of the scan for each target and non-target lesion (date of scan – date of first dose +1). Then the assessments of target and non-target lesions that occurred close to each other in time will be assigned to the same cluster.

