7.1. Tumor Response Assessments

Tumor Assessments need to include all known or suspected disease sites. Imaging to include chest, abdomen, and pelvis computed tomography (CT) or magnetic resonance imaging (MRI) scans (contrast enhanced CT/MRI is preferred unless contraindicated). Brain MRI (Gadolinium contrast enhanced) or brain CT (contrast enhanced) to be used for assessment of CNS lesions (even if brain metastases not suspected), with contingent slices of 1 mm for lesions 5 mm – 10 mm in size, 5 mm for lesions greater than 10 mm (target intracranial lesions need to be suitable for accurate measurements with a minimum size of 5 mm by MRI or CT or no less than double the slice thickness, whichever is largest). CNS imaging using MRI/CT (contrast enhanced is preferred unless contraindicated) is required at baseline in all patients and at every tumor assessment. Bone scans (or bone MRI if preferred by investigator) to be performed at baseline for all subjects and repeated every 18 ±1 weeks on study only if evidence of bone metastases is observed at baseline.

All measurable lesions up to a maximum of 2 lesions per organ and 5 lesions in total representative of all involved organs should be identified as target lesions. Exception to this rule is in the presence of CNS metastases ≥5 mm in diameter assessed by gadolinium contrasted MRI with slices of 1 mm; up to 5 CNS lesions will be permitted in addition to 5 extracranial lesions previously noted, assessed by a modified version of RECIST v1.1 ([Appendix 3](#)).

For all tumor assessments, the method of assessment that was used at baseline should be the same method used throughout the study. CT or MRI scans to be done at every 6 weeks ±1 week starting from the first dose of the investigational product while on treatment and during post-treatment follow-up period, until documented progression of disease by ICR; During post-treatment follow-up period, if applicable, bone scan (or bone MRI if preferred by investigator) to be performed every 18 weeks ±1 week until documented progression of disease by ICR. The responses will have to be confirmed ≥4 weeks after the initial response is observed. If the disease progression is suspected during the study, an unscheduled tumor assessment may be conducted before the regular tumor assessment visit, if applicable.

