6.2.6. Progression-free Survival (PFS) in Both Cohorts

Progression-Free Survival (PFS) is defined as the time from date of first dose to the date of the first documentation PD per RECIST v1.1 as assessed by the independent oncologist and investigator or death due to any cause, whichever occurs first and will be summarized in months:

$$\text{PFS (months)} = [\text{date of event or censoring} - \text{date of first dose} + 1] / 30.4375$$

PFS data will be censored as follows:

- For patients who start a new anti-cancer therapy (as defined in [Section 5.2.6](#)) prior to an event, censoring will be at the last adequate tumor assessment (see [Section 5.2](#)) prior to the start of new anti-cancer therapy. Note: if date of progression occurs on the same date as the start of new anti-cancer therapy, the progression will be counted as an event.
- For patients with documented progression or death after two or more missing tumor assessments, censoring will occur at the last adequate tumor assessment prior to the missing assessments. In this study antitumor activity will be assessed through radiological tumor assessments conducted at screening and every 6 weeks until disease progression regardless of initiation of subsequent anti-cancer therapy. The allowable time window for disease assessments is ± 7 days while on treatment and whenever disease progression is suspected (eg, symptomatic deterioration). Therefore time without adequate assessment is defined as 98 days (12 weeks plus 2 weeks).
- For patients who do not have an adequate baseline tumor assessment or who do not have any post-baseline tumor assessments, censoring will occur on the date of first dose unless death occurred on or before the time of the second planned tumor assessment (ie, on or before Day 98) in which case the death will be considered an event. Note for patients who died without any post baseline assessments and meet the definition of two or more missed assessment the reason for censoring will be documented as two or more missed assessments and censoring will occur on the date of first dose.
- All other patients alive without objective progression will be censored on the date of the last adequate tumor assessment.

The date of tumor response at each nominal timepoint based on the independent radiologist assessments will be used for determining the dates of last adequate for censoring.

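### The clustering rule for investigator tumor dates yields too few visits when no lesion was assessed at every visit, so at least two visits merge and take the earlier date

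*SAP*

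**What the plan says.** SAP 5.2.9 dates ICR and investigator assessments differently. ICR dates come from the independent radiologist. For the investigator analyses, where response or progression is derived by program from recorded lesion data, "the date of tumor assessment should be derived as the earliest scan/assessment date". Scans sit on a log page without visit labels, so they are grouped by Proc Fastclus on days from first dose.

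Three statements define the grouping:

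- What a cluster stands for: "Each cluster represents an actual visit".
- How many clusters a patient has: "For each patient, the number of clusters is equal to the maximum number of assessments available among all target and non-target lesions".
- After clustering, "the assessments of target and non-target lesions that occurred close to each other in time will be assigned to the same cluster".

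The section sets no maximum gap within a cluster, no check against planned visits, and no rule for a cluster that holds two assessments of one lesion. It names new lesions as an input to the derivation, but forms clusters from target and non-target lesions only.

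On schedule, SAP 6.2.6 has "radiological tumor assessments conducted at screening and every 6 weeks until disease progression", with a window of ±7 days. Protocol 7.1 calls for all known or suspected disease sites to be imaged; CNS imaging "is required at baseline in all patients and at every tumor assessment". If progression is suspected, "an unscheduled tumor assessment may be conducted before the regular tumor assessment visit". SAP 5.2.13 brings unscheduled tumor assessments into the efficacy analyses.

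**The concern.** The first two statements agree only if at least one recorded lesion was assessed at every visit. If each lesion missed some visit at which another was seen, there are more visits than the highest count for any single lesion, and the algorithm has to put two real visits into one cluster. The merged visit takes the earlier date, so a finding on the later scan is back-dated. The merged visit may also hold two measurements of one lesion, or make two partial assessments look like one complete assessment.

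This can arise here because body and brain are imaged separately and one can be missed without the other. Protocol 7 expects some tests to be unfeasible, and SAP 8 says COVID-19 may have affected conduct. A one-region unscheduled scan is another route if that region then misses a scheduled scan.

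At stake are investigator-assessed PFS, DoR, TTR, IC-OR and IC-DoR, so far as they are derived by program. ICR dates bypass the algorithm, so any distortion falls on the investigator side alone.

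**Working it through.** The plan states no numerical result for this rule, so there is no figure to reproduce. The rule was applied as written.

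**Inputs.** Cluster count K = most assessments of any one lesion; visit date = earliest scan in the cluster (SAP 5.2.9). Interval 42 days, window ±7 days (SAP 6.2.6). Week w falls on Day 7w + 1, so weeks 6, 12, 18 and 24 are Days 43, 85, 127 and 169. The SAP gives no Fastclus seeding or iteration options; least-squares one-dimensional k-means stands in for it.

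**Example.** Two CT lesions at weeks 6, 12 and 24; one MRI lesion at weeks 6, 18 and 24.

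- Actual post-baseline visits: 4. Each lesion has 3 assessments, so K = 3 and one pair must merge.
- Scans per day: 3, 2, 1 and 3 at Days 43, 85, 127 and 169.
- Cost of merging neighbours with n₁ and n₂ scans, d days apart: n₁n₂/(n₁+n₂) × d².

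| Merged pair | Cost |
|---|---|
| 43, 85 | (3×2/5) × 1764 = 2116.8 |
| 85, 127 | (2×1/3) × 1764 = 1176 |
| 127, 169 | (1×3/4) × 1764 = 1323 |

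Days 85 and 127 merge and are dated Day 85. Brain progression at Day 127 is then 127 − 85 = 42 days early, or 42/30.4375 = 1.38 months. Counting baseline adds one to both K and the number of visits. With baseline placed at Day −7 (an assumption), merging it with Day 43 would cost (3×3/6) × 50² = 3750, so the result stands.

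**Cases with the correct K.** There is no shortfall when all lesions are complete, when only one lesion misses a visit, when all miss the same visit, or when two lesions miss different visits but a third is complete.

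**Size within the windows.** Take two lesions with the same baseline and week-6 dates, one then missing week 12 and the other week 18.

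- Scans on Days 36, 85 and 134: merging 85 with 134 costs (1×1/2) × 49² = 1200.5, against (2×1/3) × 49² = 1600.7 for 36 with 85. Shift: 49 days.
- Scans on Days 43, 78 and 134: merging 43 with 78 costs (2×1/3) × 35² = 816.7, against (1×1/2) × 56² = 1568. Shift: 35 days, on a different pair.
- A week-15 brain scan (Day 106) replacing the week-18 one, with body imaging at Day 127: those two merge. Shift: 21 days.

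**Frequency.** The documents give no miss rate. Assume two imaging regions, V visits and independent misses with probability q per scan. The count falls short when each region has at least one visit that the other lacks:

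P = 1 − 2[1 − q(1−q)]^V + [1 − 2q(1−q)]^V

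| q (assumed) | V = 4 | V = 8 |
|---|---|---|
| 1% | 0.1% | 0.5% |
| 5% | 2.5% | 9.5% |
| 10% | 8.1% | 26.4% |

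A simulation of 200,000 patients per setting agreed to about 0.1 percentage point. These shares apply to patients with recorded lesions in two separately imaged regions. Visits missed altogether do not cause the shortfall.

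**The case against.** The strongest reply is that the trigger is narrow. Protocol 7.1 requires every site, brain included, at each assessment, so the example needs a patient with recorded brain lesions to miss brain imaging at one visit and all body imaging at another: two deviations of different kinds. A full unscheduled scan does no harm, because it raises every lesion's count and K with it. This stands, and it limits how often the fault occurs, but it does not make the rule right when it does.

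A reader might also infer more than the documents support:

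- *That any two lesions missing different visits cause a merge.* They do not if any one recorded lesion was seen at every visit.
- *That the merged pair is always known.* With two CT lesions at weeks 6, 12, 18 and 30 and an MRI lesion at weeks 6, 18, 24 and 30, merging Days 169 and 211 costs (1×3/4) × 1764 = 1323, and merging Days 127 and 169 costs the same. CT progression at Day 211 is back-dated under one solution and correctly dated under the other. Only the forced merge is certain.
- *That six weeks is a ceiling.* It is the nominal spacing; the 49-day case exceeds it.
- *That the primary result is at risk.* Primary ORR and the 28-of-66 rule use ICR assessments, which are not clustered.
- *That all investigator results, including confirmation of response, depend on clustering.* SAP 5.2.9 limits it to programmatic derivation. SAP 6.1 builds best overall response from reported timepoint responses, and SAP 5.2.12 refers to responses the investigator provided. SAP 6 nevertheless speaks of deriving these endpoints from investigator assessment. An effect on confirmation, or on the SAP 6.1.1 disagreement rate for response, is therefore possible but not established.

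**Conclusion.** The concern holds within these limits. SAP 5.2.9 treats clusters as visits but allows too few of them whenever no lesion has a complete record. The shortfall is a matter of counting and does not depend on Fastclus settings; which pair merges may.

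The error is nominally 42 days per merged pair of adjacent visits, and about 7 weeks or less within the windows. An event is dated early only if its deciding finding is on the later merged scan. The share of patients affected rests on an assumed miss rate and on independent misses: about 0.1% at 1% per scan with 4 visits, up to about 26% at 10% with 8 visits.

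The effect is confined to programmatically derived investigator results, which are descriptive and reported beside ICR versions. No study decision turns on it. It merits correction because the rule as written gives a wrong date and the remedy is cheap.

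**What to change.** Replace the cluster-count rule in SAP 5.2.9:

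1. Form visits for each patient from the union of scan dates over all lesions, including scans that show new lesions.
2. Separate visits by a maximum gap (for example, a new visit when a scan is more than 14 days after that visit's first scan), or map scans to the 6-week ±1-week grid.
3. Keep unscheduled scans as separate visits. Without this, a 14-day rule would absorb an unscheduled scan taken 10 days before a scheduled one and back-date the later finding.
4. Start a new visit whenever a lesion would otherwise have two assessments in one visit.
5. State which investigator results are derived by program and which are as reported, and align SAP 5.2.9, 5.2.12, 6 and 6.1.

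In the worked example this gives 4 post-baseline visits and dates the brain progression at Day 127. The cost is SAP wording and a simpler program, with no new data.

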5.2.10. Sum of Lesion Diameters

For lesions that are assessed as ‘too small to measure’, 5 mm will be imputed and used in the calculation of the sum of the lesion diameters.

5.2.11. Adequate Baseline

Adequate baseline for tumor data is defined using the following criteria:

- All baseline assessments must be within 28 days prior to date of first dose.
- All documented lesions must have non-missing assessments (ie, non missing measurements for target lesions and non missing lesions status at baseline for non-target lesions).

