		CYCLE 1 21 days				CYCLE 2 21 days	CYCLES ≥3 (21 days per cycle)	END of TREATMENT (EOT)/ FOLLOW-UP		
Visit Identifier ^a	Screening ¹ (≤28 days)	Day 1	Day 5	Day 8	Day 15	Day 1	Day 1	End of Treatment/ Withdrawal ²⁶	Post-Treatment Follow-Up ²⁷	Survival Follow-Up ²⁸ (every 4 months up to 3 years, then every 6 months)
Visit Time Window (days)	N/A		±3	±1	±1	±2	±2	±3	±7	±7
Other Clinical Assessments										
Serious and non-serious adverse event monitoring ²¹	X	X	→			→	→	→	→	
Concomitant medications and treatments ²²	X	X	→			→	→	→	→	X (subsequent systemic anticancer treatment)
Mood assesment ²³		X				X	X (up to Cycle 6 and then Day 1 of every other cycle)	X		
Suicidal Ideation and Behavior ²⁴		X				X	X (up to Cycle 6 and then Day 1 of every other cycle)	X		
Survival status ²⁸										X
Other Samples										
Pharmacokinetic Sampling ²⁵	See footnote ²⁵									

a. Day relative to start of study treatment (Day 1 of Cycle 1).

Abbreviations: → = ongoing/continuous event; ECG = electrocardiogram; ECOG = Eastern Cooperative Oncology Group; LVEF = left ventricular ejection fraction; MUGA = Multigate acquisition; CT = computed tomography; MRI = Magnetic Resonance Imaging; EORTC = European Organization for Research and Treatment of Cancer; ICR= Independent Central Radiology; PD = Progression of Disease; ALK = anaplastic lymphoma kinase; PE = Physical examination; CTCAE = Common Terminology Criteria for Adverse Events; HBV = Hepatitis B Virus; HCV = Hepatitis C Virus; QD = Quaque Die (every day); CCI N/A = Not applicable.

Footnotes:

Acceptable time windows for performing each assessment are described in the column headers.

1. Screening: To be obtained within 28 days prior to enrollment (Cycle1Day1: C1D1). Available results for assessments that have been performed prior to informed consent being obtained as part of the patient's on-going routine standard of care testing (laboratory tests or tumor imaging scans) may be used to satisfy patient eligibility assessment, provided they have been performed within the required timing (that is 7 days prior enrollment for laboratory tests or 28 days prior enrollment for tumor imaging or 6 weeks prior enrollment for bone scan [or bone MRI if preferred by investigator]) and meet the related criteria.
2. Informed Consent: Must be obtained prior to undergoing any study-specific procedures. CCI [REDACTED]

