12. Pregnancy Test: For female subjects of childbearing potential, a serum or urine pregnancy test, to be performed on two occasions prior to starting study therapy, once at the start of screening and once at the baseline visit, whose results must be available before investigational product administration. Pregnancy tests also routinely repeated at every cycle during the active treatment period, at the end of study therapy and additionally whenever one menstrual cycle is missed or when potential pregnancy is otherwise suspected. Additional pregnancy tests if requested by IRB/IECs or by local regulations.
13. Triplicate 12-lead ECGs: At each time point, 3 consecutive 12-lead ECGs performed approximately 2 minutes apart (or within 10 minutes, whichever is appropriate) to determine PR interval and mean QTc interval. The ECG must occur prior to any blood sample collections or venipuncturing if conducted on the same day, except for the specific requirement in the protocol. ECGs are to be collected at predose and 1-4 hours post-dose on Cycle 1 Day 1. ECGs will also be collected at 1-4 hours post-dose on Cycle 1 Day 8 and Day 15, and on Cycle 2 Day 1. Single reading ECG are to be collected pre-dose on Day 1 of Cycle 3 and every other cycle thereafter. ECGs at later cycles are to be collected as clinically indicated. At End of Treatment/Withdrawal, triplicate ECGs are to be collected. Additional ECG time points may be performed based on the emerging data.
14. IRT registration: Study treatment should be initiated preferably on the randomization day but no later than 1 days after randomization.
15. Left ventricular ejection fraction (LVEF) Assessment: Echocardiogram (ECHO) or multigated acquisition scan (MUGA) to be performed at Screening, at pre-dose, on Cycle 1 Day 1 and every other cycles thereafter, and at the EOT visit. The same method should be used at each time point. If the screening ECHO or MUGA is normal and has been performed within 2 weeks prior to randomization, there is no need to repeat this assessment at Day 1 of Cycle 1. At subsequent visits a time window of 1 week prior to Day 1 of subsequent cycles will be permitted for the ECHO/MUGA assessment.

16. **Treatment compliance check:** The study site must follow up (for example, via a telephone call) with each subject on Cycle 1 Day 5 (± 3 days) to confirm that the subject understands and is in compliance with lorlatinib dosing instructions.

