5.1. Allocation to Treatment

The investigator's knowledge of the treatment should not influence the decision to enroll a particular subject or affect the order in which subjects are enrolled.

A subject must sign an informed consent document (ICD) before being evaluated for study entry. Once a subject who has met inclusion and exclusion criteria has provided a signed ICD, allocation of subjects to lorlatinib treatment will proceed through the use of an interactive response technology (IRT) system (interactive Web-based response [IWR]). The site personnel (study coordinator or specified designee) will be required to enter or select information including but not limited to the user's identification (ID) and password, the protocol number, and the subject number. The site personnel will then be provided with a treatment assignment, randomization number, and dispensable unit (DU) or container number when investigational product is being supplied via the IRT system. The IRT system will provide a confirmation report containing the subject number, randomization number, and DU or container number assigned. The confirmation report must be stored in the site's files.

The study-specific IRT reference manual will provide the contact information and further details on the use of the IRT system.

Qualified subjects will be enrolled to the study to receive lorlatinib monotherapy at the RP2D of 100 mg QD, administered as 4×25 mg oral tablets, continuously. Study treatment should be initiated preferably on the randomization day but no later than 1 day after randomization.

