7. ASSESSMENTS

Every effort should be made to ensure that the protocol-required tests and procedures are completed as described. However, it is anticipated that from time to time there may be circumstances outside of the control of the investigator that may make it unfeasible to perform the test. In these cases, the investigator will take all steps necessary to ensure the safety and well-being of the subject. When a protocol-required test cannot be performed, the investigator will document the reason for this and any corrective and preventive actions that he or she has taken to ensure that normal processes are adhered to as soon as possible. The study team will be informed of these incidents in a timely manner.

Available results for assessments that have been performed prior to informed consent being obtained as part of the patient's on-going routine standard of care testing (laboratory tests or tumor imaging scans) may be used to satisfy patient eligibility assessment, provided they have been performed within the required timing (that is 7 days prior enrollment for laboratory tests or 28 days prior enrollment for tumor imaging or 6 weeks prior enrollment for bone scan [or bone MRI if preferred by investigator]) and meet the related criteria.

End of treatment (EOT) visit should be performed no later than 4 weeks (+1w) from the last dose of investigational product or when decision taken to provide alternative anti-cancer therapy, whichever is sooner.

For samples being collected and shipped, detailed collection, processing, storage, and shipment instructions and contact information will be provided to the investigator site prior to initiation of the study.

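### SAP 5.2.11 requires all baseline tumor imaging within 28 days of first dose, but the protocol accepts a reused bone scan up to 6 weeks old, so a compliant patient's PFS could be censored at first dose

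*SAP*

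**What the plan says.** **SAP definition.** SAP 5.2.11 sets two conditions for an adequate tumor baseline. The first is timing: "All baseline assessments must be within 28 days prior to date of first dose". The second is completeness: "All documented lesions must have non-missing assessments". Neither makes an exception for bone imaging.

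**Protocol windows.** Protocol Section 7 and Schedule of Activities footnote 1 let sites reuse routine-care scans done before consent, with two separate limits: "28 days prior enrollment for tumor imaging or 6 weeks prior enrollment for bone scan". The bone limit also covers bone MRI. Footnote 17 lists bone imaging within the tumor assessments, and Section 7.1 requires it at baseline for all subjects. No repeat is required when an older scan is reused.

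**Consequence.** Under SAP 6.2.6 and Table 2, a patient without an adequate baseline is censored for PFS on the date of first dose, except that a death by Day 98 counts as an event. Table 3 ranks this censoring reason first.

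**The concern.** The protocol tells sites that bone imaging up to 42 days old is acceptable; the SAP appears to treat anything older than 28 days as a failed baseline. A patient handled exactly as the protocol allows could therefore lose all PFS follow-up. Later scans every 6 weeks, and bone imaging every 18 weeks where bone metastases were present, would be collected but not used for PFS. The best-overall-response rules in SAP 6.1 do not refer to 5.2.11, so the same patient could be a confirmed responder with a duration of response and still contribute nothing to PFS.

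If the loss falls mainly on patients with bone lesions, it is not spread evenly over the cohort.

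**Working it through.** **The plan's own figures.** SAP 6.2.6 allows 12 weeks plus 2 weeks without adequate assessment: 12 × 7 + 14 = 98 days, as stated. The only powered figure, at least 28 responses among 66 with ORR 30% against 50%, also reproduces by exact binomial: P(X ≥ 28 | 0.30) = 0.0216, power at 0.50 = 0.912. A cut-off of 27 would give 0.0386, so 28 is correct. None of this depends on the baseline window.

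**The gap.**
- Protocol limit for reused bone imaging: 6 × 7 = 42 days before enrollment. Footnote 1 equates enrollment with Cycle 1 Day 1.
- SAP limit: 28 days before first dose.
- Gap: 42 − 28 = 14 days, that is, imaging 29 to 42 days old.

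Take a scan at the midpoint, (28 + 42)/2 = 35 days. It is 7 days inside the protocol limit and 7 days outside the SAP limit.

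**PFS assigned.** SAP 6.2.6 computes (date of event or censoring − date of first dose + 1)/30.4375. Censoring at first dose gives (0 + 1)/30.4375 = 0.033 months, whatever progression is documented later.

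**Which analysis is reached.**
- *Investigator-assessed PFS.* SAP 5.2.9 takes the earliest scan date as the assessment date and groups scans by days from first dose "to the date of the scan for each target and non-target lesion". Protocol Appendix 3 requires all other sites of disease to be recorded as non-target lesions at baseline. A bone lesion recorded from the older scan thus carries a date outside 28 days.
- *Centrally assessed PFS.* SAP 5.2.9 uses the radiologist's date for each nominal timepoint. It does not say how a baseline made up of scans from different days is dated, so the result is undetermined.
- *Negative bone scan.* On the literal wording of 5.2.11 it counts as a baseline assessment. But that section concerns tumor data and documented lesions, and a negative scan may leave no lesion record, so it is less likely to trigger the rule.

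**Possible size.** The documents give no frequencies, so every share here is an assumption. Let b be the share with a bone lesion and e the share of those with early, unrepeated bone imaging; f = b × e. Rough widening of the PFS confidence interval is 1/√(1 − f) − 1.

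| b × e | f | of 66 | of 34 | CI widening |
|---|---|---|---|---|
| 0.2 × 0.1 | 2% | 1.3 | 0.7 | 1.0% |
| 0.2 × 0.25 | 5% | 3.3 | 1.7 | 2.6% |
| 0.4 × 0.25 | 10% | 6.6 | 3.4 | 5.4% |
| 0.4 × 0.5 | 20% | 13.2 | 6.8 | 11.8% |

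The last row is an extreme. The widening formula assumes events are lost in proportion to patients; Kaplan-Meier precision depends mainly on events, so it is only a guide.

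**The case against.** **The SAP may mean to be stricter.** SAP 3.4 announces a separate adequate-baseline definition for tumor endpoints, Protocol Section 9 lets the SAP modify the outline, and SAP version 2.0 revised 5.2.11. The 6-week allowance is also worded as serving eligibility. This shows that the SAP may differ. It does not show that this difference was intended: no reason is given for rejecting imaging the protocol accepts, and with no repeat required the reused scan is the only baseline bone imaging.

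**Bone scans may lie outside the rule.** The protocol sentence separates tumor imaging from bone scan, and bone scan is not among the methods listed for measurable disease in SAP 5.2.8. A bone-scan lesion would thus be at most non-target. This narrows the point but does not remove it, because the rule says all baseline assessments and footnote 17 places bone imaging among them.

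**The route is narrow and visible.** It needs a pre-consent scan, 29 to 42 days old, not repeated, and most plausibly with a lesion recorded from it. SAP 6.4.1 tabulates adequate baseline and Table 3 the censoring reason. Text after the PFS rules is redacted, so a supportive analysis may exist. All this stands and limits the weight of the point, though tabulating a loss does not restore the follow-up.

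**Stronger readings that the documents do not support.** A reader might infer that affected patients also become non-responders, since SAP 6.1 and Protocol 9.3.1 treat inadequate tumor data as non-response. The examples there are absent baseline or absent follow-up, and neither the response rules nor the listed reasons for a not-evaluable response mention baseline timing. A reader might also infer that CT/MRI needs a new anchor, because dosing may start one day after randomization. Footnote 1 already equates enrollment with Cycle 1 Day 1, and the bone-imaging mismatch can be resolved without that change.

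**Conclusion.** The two windows conflict and nothing elsewhere in the documents reconciles them. Applied literally, SAP 5.2.11 could remove the PFS follow-up of a patient who met every protocol requirement. That is a possible consequence for a narrow group, not an established loss. It is clearest for investigator-assessed PFS with a bone lesion recorded from the older scan, and open for centrally assessed PFS.

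At the assumed 2% to 5%, about 1 to 3 patients in Cohort 1 and 1 to 2 in Cohort 2 would contribute no PFS follow-up, with intervals roughly 1% to 3% wider. No direction of bias is shown. PFS is secondary and carries no hypothesis test; ORR, the sample size of 66, alpha and the cut-off of 28 are not shown to be affected. The point is small but worth settling before database release.

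**What to change.** Amend SAP 5.2.11 to keep 28 days for CT/MRI, including brain, and to accept bone scan or bone MRI within the protocol's 6-week window. Add that bone imaging within that window does not by itself make the baseline inadequate. The change should apply to both investigator and central assessments, so that the result does not turn on how the baseline date is assigned.

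The cost is one or two SAP sentences and a programming parameter. The downside is that slightly older bone imaging counts as baseline, which the protocol already allows.
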